5.1 Target parameters

5.1.1 Primary and secondary endpoints

Primary endpoint:

- Proportion of patients still being treated at the time of the 12-month visit with the initially allocated anticoagulant, defined as Kaplan Meier estimate at 12 months for persistence, stratified for dabigatran etexilate and VKA. Persistence is defined as the time between initiation and permanent termination of therapy ⁽²⁰⁾. The start of treatment (documented in the CRF of visit 1) is documented as the start date and the date of discontinuation of treatment with Pradaxa® or VKA as the time of permanent termination of therapy

Secondary endpoints:

- Proportion of patients with low, medium or high adherence at the time of the 6-month visit, stratified for dabigatran etexilate and VKA; categorisation is done on the basis of the Morisky questionnaire.
- Reasons for permanent treatment discontinuation.

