6.1 Timetable of visits

Following information and consenting, patient data on sociodemographic factors, previous history including risk of stroke and bleeding and the patients' prior and concomitant medication will be recorded at visit 1 as part of this NIS.

AF patients will use Pradaxa® or VKA in accordance with the respective Summaries of Product Characteristics.

Treatment with Pradaxa® or VKA will be recorded approximately quarterly over the observation period of 12 months (at a regular visit after about 3, 6, 9 and 12 months).

In addition, any emergent adverse events will be documented at these visits and discontinuation and any reasons for discontinuation recorded.

Reasons for discontinuation include intolerable adverse events, intolerance or insufficient efficacy of treatment with dabigatran etexilate or VKA.

After about 6 months of observation, in addition to the continuation of therapy, treatment adherence will be investigated and documented by means of the Morisky questionnaire at a regular follow-up visit.

The patient has the right to end their participation in the NIS at any time without giving a reason.

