The analysis is performed on the basis of the patient cohorts resulting from the 1:1 matching. Kaplan Meier estimates for the time to discontinuation of treatment (cf. definition in section 5.1.) will be calculated separately for the dabigatran and the VKA patient group and illustrated graphically. In particular, the Kaplan Meier estimates for persistence at time 3, 6, 9 and 12 months will be reported. The comparison in terms of the persistence of patients on treatment with dabigatran versus VKA will be performed by means of the stratified log-rank test, which takes account of the dependency of treatment groups resulting from matching (cf. Klein, Moeschberger, 1997, ²²). Patients who discontinued the study prematurely and for whom no treatment discontinuation is documented will be censored at the time of study discontinuation. Patients who end the study as planned will be censored on the day after the last visit if no previous treatment discontinuation is documented.

The absolute number and proportion of patients discontinuing the initial treatment in the course of the study will be summarised overall and according to the reasons for discontinuation for the dabigatran and VKA cohorts.

The association of patient characteristics (including treatment allocation) with persistence will be investigated by means of Cox regression models (univariate and multivariate models). Baseline characteristics will be presented stratified for patients who discontinue the treatment in the course of the study and those who do not.

A multivariable Cox regression model (including the factors used for calculating the PS and choice of treatment) will be reported as a sensitivity analysis. For this analysis, all patients who are within the common supports of the empirical density function of the PS (instead of matched pairs) will be included; the common support is determined after excluding patients with a propensity score above the 97.5% percentile and below the 2.5% percentile in each treatment group in order to avoid a strong influence from patients with extreme PS values.

Adherence

The analysis is performed on the basis of the patient cohort resulting from 1:1 matching. The Morisky questionnaire consists of 8 questions and will be presented at the time of the 6-month visit. The analysis and categorisation of patients into the categories

- poor adherence (score >2)
- medium adherence (score=1, 2) and
- high adherence (score=0)

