5. ENDPOINT(S)

5.1 PRIMARY ENDPOINT(S)

Proportion of patients, who are still treated with the initial assigned anticoagulant at 12-months visit, derived by Kaplan-Meier estimator for persistence at 12 months, stratified for dabigatran etexilate and VKA. Persistence is defined as the time in months between initiation, i.e. date of first visit, and permanently discontinuation of treatment with Pradaxa® or VKA. Patients who discontinue study prematurely and without documented treatment discontinuation will be censored at date of study termination. Patients completing the study as planned will be censored at the day after last visit, if no earlier treatment discontinuation is documented.

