6.6 HANDLING OF MISSING DATA AND OUTLIERS

Missing or incomplete AE dates are imputed according to BI standards (see “Handling of missing and incomplete AE dates”). All available data will be used in the data analysis. Drop-outs will be adequately reflected because of the underlying method (survival analysis). Missing values will be categorized as “Missing” and will not be imputed.

Outliers will not be excluded from analysis.

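### Death on the initial drug is not classified in the persistence endpoint; if it is censored, the 12-month Kaplan-Meier value overstates the proportion still being treated

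*SAP*

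**What the plan says.** Both documents describe the primary endpoint as a share of patients. Protocol 5.1.1 has "Proportion of patients still being treated at the time of the 12-month visit with the initially allocated anticoagulant"; SAP 5.1 has "Proportion of patients, who are still treated with the initial assigned anticoagulant at 12-months visit, derived by Kaplan-Meier estimator for persistence at 12 months".

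The event is a recorded stop. Protocol 5.1.1 takes "the date of discontinuation of treatment with Pradaxa® or VKA as the time of permanent termination of therapy". The censoring rule in Protocol 7.3 is: "Patients who discontinued the study prematurely and for whom no treatment discontinuation is documented will be censored at the time of study discontinuation". SAP 5.1 gives the same rule ("Patients who discontinue study prematurely and without documented treatment discontinuation will be censored at date of study termination") and SAP 7.4 repeats it. On drop-outs in general, SAP 6.6 says: "Drop-outs will be adequately reflected because of the underlying method (survival analysis"); Protocol 7.4 takes the same line.

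Death is not named in any of these places. Protocol 6.1 states: "Reasons for discontinuation include intolerable adverse events, intolerance or insufficient efficacy of treatment with dabigatran etexilate or VKA". That list is open-ended and does not mention death. Death appears only on the safety side: as a seriousness criterion in Protocol 5.2.2.1, and as fatal codes for outcome and seriousness on the (S)AE form in Protocol Attachment 2. That form's field for action taken with the product offers both discontinued and not applicable, so it does not settle how a fatal case is treated.

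**The concern.** A patient who dies while taking the drug can fall under either rule, depending on whether a stop date was entered. The two outcomes estimate different things. Counting the death as a stop gives the proportion alive and on drug, but records a death as a discontinuation and carries it into the secondary endpoint on reasons for discontinuation. Censoring the death gives persistence as it would be if nobody died, which is not what the label says.

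The general statement that survival analysis takes care of drop-outs does not resolve this. A patient lost to follow-up has an unknown treatment status, whereas a patient who has died has a known one. The cohort has atrial fibrillation, and the SAP has an age class of 75 and over, so some deaths within a year should be expected. At stake is mainly whether the headline percentage in each arm means what it is called. Secondarily, the subgroup percentages by age, previous stroke and CHA₂DS₂-VASc score may be overstated by different amounts if mortality differs across those classes.

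**Working it through.** **Inputs from the documents.** Persistence at 12 months: 63% for dabigatran, and 51%, 53.8% or 56.5% for VKA (Protocol, Local Amendment 1, Change 3). Matched patients: 2 × 0.66 × 800 = 1056, which reproduces the stated total and gives 528 per arm. Drop-outs and missing values: 15% at one year, with deaths not separated.

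**Input not in the documents.** 12-month mortality m. I assume 2% to 8%.

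The plan has no figure on deaths to reproduce. Its power figures were checked with Schoenfeld's formula and exponential drop-out: 97.2%, 84.4% and 55.7% against the stated 97.8%, 84.8% and 61.1%. The third does not reproduce, but nothing here depends on it.

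**Formulas.** Let S be 12-month persistence in the absence of death, and let death and stopping have independent constant hazards.

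- Kaplan-Meier with deaths censored: S
- Alive and on drug: S × (1 − m). Kaplan-Meier with deaths counted as stops gives the same value.
- Overstatement when deaths are censored: S × m

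| S | m | Deaths censored | Alive and on drug | Overstatement (points) |
|---|---|---|---|---|
| 63% | 2% | 63.0% | 61.74% | 1.26 |
| 63% | 5% | 63.0% | 59.85% | 3.15 |
| 63% | 8% | 63.0% | 57.96% | 5.04 |
| 51% | 2% | 51.0% | 49.98% | 1.02 |
| 51% | 5% | 51.0% | 48.45% | 2.55 |
| 51% | 8% | 51.0% | 46.92% | 4.08 |

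**Three-way split at S = 63%, m = 5%.** The hazards are −ln 0.63 = 0.462 for stopping and −ln 0.95 = 0.051 for death. The proportion off drug for either reason is 1 − 0.5985 = 40.15%. A share 0.051/0.513, about one tenth, is death on drug: 4.0%, or about 21 of 528. The rest, 36.1%, is stopping. On drug 59.9%, stopped 36.1% and dead on drug 4.0% add to 100%. For VKA at 51% the same steps give about 19 deaths on drug among 528.

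**Effect on the comparison.**

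- *Equal mortality, uniform coding.* The difference between arms is multiplied by (1 − m). A difference of 12 points becomes 11.76, 11.40 or 11.04; one of 6.5 points becomes 6.37, 6.18 or 5.98. The change is 0.13 to 0.96 points.
- *Mortality differs by arm.* The difference in proportions alive and on drug is (S_D − S_V) − (S_D × m_D − S_V × m_V), where D is dabigatran and V is VKA. The two overstatements then no longer shrink the difference in proportion.
- *Coding differs completely by arm.* With S = 63% in both arms and no true difference, censoring deaths in one arm and counting them in the other creates a gap of S × m, or 1.3 to 5.0 points. This is a bound, not an expectation.

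**The case against.** The strongest reply is that the plan does contain a default. A death with no stop date is a premature study end without documented discontinuation, so it is censored. Protocol 5.1.1 also defines the endpoint as a Kaplan-Meier estimate of time to permanent termination, and censoring death is a legitimate cause-specific reading of that. The eCRF pages for stopping and study end are not in the documents and may hold a code for death. Sites are trained, entries are checked, and source data are compared at about 10% of sites. All analyses are declared descriptive.

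Much of this stands. A reader might infer that the plan has no rule at all that could apply to death, or that both possible codings are wrong. The documents do not support either: a default exists, and counting deaths as stops reproduces exactly the literal proportion alive and on drug. A reader might also infer that sites do code deaths inconsistently. That is possible under the text but unproven without the eCRF.

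Nor should the 1 to 5 point shift within an arm be set against the planned differences of 6.5 to 12 points between arms, because they are different quantities. Each site alternates dabigatran and VKA patients 1:1, so a site's habit tends to affect both arms. Matching on a propensity score planned to include age, previous stroke, CHA₂DS₂-VASc and HAS-BLED should narrow mortality differences. These features limit a differential effect but do not rule it out, since physicians choose the drug.

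What does not stand is the appeal to default or to descriptive status. The default is silent on a fatal case with a stop date. Where it does apply, it yields a figure that does not match its label, and a descriptive percentage still has to describe what it is called. An eCRF code for death would still need an SAP rule to use it.

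**Conclusion.** The point holds as a gap in classification and a mismatch between estimate and label. If deaths on drug are censored, the 12-month value overstates the proportion still being treated by S × m: 1.3, 3.2 or 5.0 points at 63% persistence for mortality of 2%, 5% or 8%. The mortality range is my assumption, and the formula assumes that death and stopping are independent. It also compares all deaths censored with all counted; mixed coding gives a value in between.

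The documents do not support the stronger conclusion that the comparison of dabigatran with VKA is materially biased. With equal mortality and uniform coding, the difference moves by about 0.1 to 1.0 point. Anything larger needs mortality or coding to differ by arm, which the design limits but does not exclude. The change should be made, but the plan's main comparison does not fail without it.

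**What to change.** In SAP 5.1 and 7.4:

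- State that a death on the initial drug, identified from the fatal-outcome record whatever stop date is entered, is a competing event and neither a discontinuation nor a drop-out. Define how a stop date shortly before death is classified.
- Report per arm, at 3, 6, 9 and 12 months, the proportions on drug, stopped, and dead on drug, using cumulative incidence.
- Keep the stratified log-rank test and the Cox models as cause-specific analyses that censor at death. Label the Kaplan-Meier value as cause-specific persistence.

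In SAP 7.5, count deaths on drug separately from the reasons for discontinuation.

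For deaths without a stop date, the log-rank and Cox analyses do not change. The gain is one uniform classification and a correctly labelled 12-month proportion. The cost is some SAP wording, a standard SAS procedure on data already collected, and a slightly lower reported proportion still treated. No visits or patients are added.

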5.2 SECONDARY ENDPOINT(S)

- Proportion of patients with low, medium or high adherence at 6-months visit stratified for dabigatran etexilate and VKA. Categorisation of patients into low, medium or high adherence is done according to Morisky
- Reasons for permanent discontinuation of therapy

5.3 FURTHER ENDPOINT(S)

Not applicable.

5.4 OTHER VARIABLE(S)

Other variables will be baseline characteristics (incl. risk score for stroke and bleeding, this means CHA₂DS₂-VASC and HAS-BLED) and patient's characteristics such as age, gender, height, weight, BMI, education, marital status and health insurance. Additionally information about previous diseases, medical progress and follow-up will also be collected.

6. GENERAL ANALYSIS DEFINITIONS

6.1 TREATMENT(S)

Evaluation/ Method	Visit 1 (Baseline)	Visit 2 (after approx. 3 month)	Visit 3 (after approx. 6 month)	Visit 4 (after approx. 9 month)	Visit 5 (after approx. 12 month)
Socio demography	X				
VHF- anamneses	X				
CHA ₂ DS ₂ VASc- / HAS-BLED- Score	X		X		X
Further comorbidities	X		X		X
Date of start of therapy of Dabigatran etexilate/ VKA (incl. dosing)	X				
Concomitant medication (incl. intake frequency)	X		X		X
Treatment with initial oral anticoagulation		X	X	X	X
Morisky-Score			X		
Date of discontinuation (incl. reason)		X	X	X	X
In case of abortion: therapy after discontinuation		X	X	X	X
Adverse events*		X	X	X	X

* AE data will be collected until 30 days after end of therapy

6.2 IMPORTANT PROTOCOL VIOLATIONS

Table 6.2: 1 Important protocol violations

Category/ Code		Description	Requirements	Excluded from
A		Entrance criteria not met		
	A1.1	Inclusion criteria not met	Inclusion criteria not met as specified in the protocol.	FAS
	A2	Exclusion criteria not met	Exclusion criteria not met as specified in the protocol	None
B		Informed consent		
	B1	Informed consent not available/not done	Informed consent date missing	All

Patients who received oral anticoagulants for less than 2 months before study inclusion will be treated as minor protocol deviations. These patients will be further documented and the inclusion criterion regarding the prior treatment with anticoagulants will not be set to 'No'. Subjects who were previously treated with oral anticoagulants for two months or more are excluded from the efficacy analysis.

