3.3.1 Main diagnosis

Four thousand patients with non-valvular atrial fibrillation, in whom anticoagulant treatment with Pradaxa® or VKA is indicated in accordance with the guidelines and in line with the Summary of Product Characteristics, must be observed in about 1000 practices (community-based cardiologists and primary care internists / general practitioners) in this NIS.

Before the start of therapy with Pradaxa® or VKA, due note must be taken of the contraindications. See also the respective current Summaries of Product Characteristics of Pradaxa® or the VKA used.

Patients treated with VKA must also theoretically be treatable with dabigatran etexilate to ensure comparability of the patient populations.

3.3.2 Inclusion criteria:

Patients can be included if all the following criteria are present:

- Newly prescribed treatment with Pradaxa® (dabigatran etexilate)/VKA in the indication "Stroke prevention in non-valvular atrial fibrillation" (AF) respecting the indication and contraindications as described in the respective Summary of Product

Characteristics Pradaxa® 110 mg or 150 mg hard capsules or the appropriate VKA (patients are eligible for both Pradaxa® and VKA therapy).

- Only patients who are eligible *both* for therapy with Pradaxa® *and* for therapy with VKA in accordance with the respective Summaries of Product Characteristics are documented (patients eligible for VKA *and* Pradaxa®)
- Treatment with dabigatran etexilate or VKA is given in accordance with the respective Summaries of Product Characteristics. The routine diagnostic procedures and treatment that would be undertaken irrespective of the study are unaffected.
- Only patients on VKA therapy who would also be eligible for therapy with dabigatran etexilate in accordance with the Pradaxa® Summary of Product Characteristics are documented.
- Patients must have signed the patient consent form before inclusion in the NIS.

3.3.3 *Exclusion criteria*

- Patients with the general and special contraindications mentioned in the packaging leaflet or Summary of Product Characteristics must not be included.

The Summaries of Product Characteristics for Pradaxa® are contained in the NIS study folder in the register "Summaries of Product Characteristics".

For the selected VKA, the observing physician must use the current Summary of Product Characteristics of the product concerned for guidance.

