4.1 Administered medications

4.1.1 Products

Treatment-naive AF patients will be treated with Pradaxa® hard capsules or VKA in accordance with the Summary of Product Characteristics:

Direct oral thrombin inhibitor:	Pradaxa® 150 mg hard capsules Pradaxa® 110 mg hard capsules
Vitamin K antagonists	e.g. phenprocoumon

Pradaxa® 150 or 110 mg hard capsules contain dabigatran etexilate (active substance: dabigatran).

The choice of VKA is at the discretion of the observing physician. There is no set dosage for these products.

The Summaries of Product Characteristics for Pradaxa® are contained in the NIS study folder in the register "Summaries of Product Characteristics".

For the selected VKA, the observing physician must use the current Summary of Product Characteristics of the product concerned for guidance (www.fachinfo.de).

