6.3 PATIENT SETS ANALYSED

Treated Set (TS): All patients with at least one documented prescription of dabigatran etexilate or VKA.

Full Analysis Set (FAS): All patients from the Treated Set with main diagnosis non-valvular atrial fibrillation and who have at least one evaluable efficacy endpoint.

Matched group (MG): Patient cohort resulting from the 1:1 matching based on FAS.

Table 6.3: 1 Patient sets analysed

Class of endpoint	TS	MG
Primary and secondary endpoint		X
Safety endpoints	X	
Demographic/baseline	X	X

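### Patients with under two months of prior oral anticoagulation enter the matched primary persistence analysis, and no planned model, subgroup or sensitivity analysis takes that prior use into account

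*SAP*

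**What the plan says.** On who is studied, protocol 4.1.1 states "Treatment-naive AF patients will be treated with Pradaxa® hard capsules or VKA in accordance with the Summary of Product Characteristics". The inclusion criterion in protocol 3.3.2 begins "Newly prescribed treatment with Pradaxa® (dabigatran etexilate)/VKA in the indication" and sets no limit on earlier exposure.

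On how earlier exposure is handled, SAP 6.2 has two rules:

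- Under two months: "Patients who received oral anticoagulants for less than 2 months before study inclusion will be treated as minor protocol deviations". The relevant inclusion criterion is not to be marked as failed.
- Two months or more: "Subjects who were previously treated with oral anticoagulants for two months or more are excluded from the efficacy analysis".

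Neither rule says which anticoagulant the patient had been taking. SAP 6.3 defines the set for the primary and secondary endpoints as "Patient cohort resulting from the 1:1 matching based on FAS". SAP 4 reports no change to the planned analysis.

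On adjustment, protocol 7.3 asks that every baseline variable expected beforehand to be associated with persistence or adherence go into the propensity model. SAP 7.4 lists CHA2DS2-VASc, HAS-BLED, age and previous stroke. On data, protocol 6.1 says "prior and concomitant medication will be recorded at visit 1".

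**The concern.** The primary endpoint is time to permanent stop of the initial anticoagulant. A patient's recent history with an anticoagulant is close to that outcome, and the rule can admit two kinds of pre-treated patient:

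- **Switchers.** Someone who stopped one drug within two months and was then enrolled on the other. If they also tend to stop the second drug sooner, the arm that receives them looks less persistent.
- **Same-drug users.** Someone already taking the study drug for some weeks at visit 1. SAP 5.1 takes the first visit as initiation. If stops cluster early, these patients are already past the riskiest weeks, and their arm looks more persistent.

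Either kind can be matched to a patient with no earlier anticoagulant, because nothing in the match looks at prior use. What is at stake is whether the matched contrast describes the two drugs or partly the mix of pre-treated patients in each arm.

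**Working it through.** **1. Route into the primary analysis.** In SAP Table 6.2: 1, code A1.1 (inclusion criteria not met) removes a patient from the FAS. With under two months of prior use the criterion stays met, so A1.1 is not triggered. The patient stays in the FAS, from which the matched group is drawn.

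**2. Is prior use handled anywhere?**

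| Planned element (SAP 7.4) | Variables | Prior anticoagulant |
|---|---|---|
| Propensity score | CHA2DS2-VASc, HAS-BLED, age, previous stroke | no |
| Common-support sensitivity Cox model | the same plus treatment | no |
| Univariate and stepwise Cox models | the same plus specialty and treatment | no |
| Persistence subgroups | scores, age, stroke, specialty, dabigatran dose | no |
| Naive-only analysis | not planned | no |

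HAS-BLED includes labile INR, a weak trace of earlier VKA use. It enters only as <3 or ≥3 and does not stand in for prior use.

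**3. The plan's own figures.** The documents give no share of pre-treated patients. The figures that bear on size are in the power table in Local Amendment 1: 63% persistence on dabigatran; 51%, 53.8% or 56.5% on VKA; 15% drop-out; matched N = 2 × 0.66 × 800 = 1056, or 528 per arm. The planned differences are 12, 9.2 and 6.5 points.

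I used Schoenfeld's formula with exponential stopping and drop-out: λ = −ln S, δ = −ln 0.85, events per arm = n·λ/(λ+δ)·(1 − e^−(λ+δ)), HR = ln 0.63 / ln S_VKA, power = Φ(½√events·|ln HR| − 1.96). The result is 97.2%, 84.4% and 55.7%, against the stated 97.8%, 84.8% and 61.1%. The first two cells agree closely and the third does not. That mismatch is a separate matter, and nothing below rests on it.

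**4. Illustration: switchers in one arm only.** The share f and hazard ratio HR are assumptions. Arm persistence = (1−f)·63% + f·63%^HR, with 63%^1.5 = 50.0% and 63%^2 = 39.7%.

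| f | shift at HR 1.5 | shift at HR 2 |
|---|---|---|
| 5% | −0.65 points | −1.17 points |
| 10% | −1.30 points | −2.33 points |
| 20% | −2.60 points | −4.66 points |

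At f = 10% this is 1.30/6.5 = 20% to 2.33/6.5 = 36% of the smallest planned difference. With no true difference and 10% of one arm persisting at 40% to 50%, the chance of p ≤ 0.05 rises from 5% to about 7% to 12%.

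**5. Offsets.** If both arms hold 10% switchers with the same HR around the same 63%, the shifts cancel. With 10% in one and 5% in the other at HR 2, the net is 2.33 − 1.17 = 1.16 points.

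For same-drug users, assume Weibull stopping with shape k and 63% at 12 months. Persistence over the next 12 months after u months already on drug is exp(−λ[(12+u)^k − u^k]), with λ = −ln 0.63 / 12^k. For u = 1 and 2 this gives 66.5% and 68.2% at k = 0.7, and 70.6% and 73.3% at k = 0.5. With a constant hazard (k = 1) it stays at 63%. Ten per cent of such patients in one arm would move it by 0.10 × (66.5 − 63) = +0.35 to 0.10 × (73.3 − 63) = +1.03 points, opposite in sign to step 4.

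**6. Precision of a naive-only matched cohort.** By the method of step 3, at 53.8% VKA persistence:

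| Pre-treated share removed | N | Power |
|---|---|---|
| 0% | 1056 | 84.4% |
| 5% | about 1003 | 82.5% |
| 10% | about 950 | 80.4% |
| 20% | about 844 | 75.7% |

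**The case against.** A reader might infer that the SAP breaches a treatment-naive entry criterion. The documents do not go that far. The phrase is in the product description in protocol 4.1.1. The listed criterion says newly prescribed, and protocol 7.1 speaks of recent prescription. The analysis population in protocol 7.3 has no naive restriction, so against that text SAP 6.2 tightens the population by removing longer prior use. What stands is an unreconciled wording: the SAP refers to an inclusion criterion on prior anticoagulation that the protocol does not list separately, and the two-month limit appears only in the SAP.

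A reader might also infer that early failures on one drug enter as new starters on the other, with bias in a known direction. The rule permits this but does not show it. It does not name the prior drug, and patients must be eligible for both drugs, so a stop caused by a contraindication to either would bar entry. Switching can go both ways, and same-drug use can push upward. The study is also declared descriptive. That lowers the stakes of a p-value, but it does not remove bias from a comparison that is the primary objective.

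On data, the visit 1 list in protocol 6.2 and the flowchart name only concomitant medication, so it is not certain that the prior drug is captured. However, applying the two-month rule already requires whether and for how long a patient was treated.

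**Conclusion.** The point holds as a gap in the analysis plan. Patients with under two months of prior oral anticoagulation can enter the matched primary comparison, and a plausible confounder, within the protocol's own rule for choosing propensity variables, is left out of every planned analysis. The comparison may be biased.

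Neither the size nor the net direction can be stated from the documents. The 1.3 to 2.3 points at 10% switchers is an illustration that rests on an assumed share, an assumed hazard ratio of 1.5 to 2, and switchers in one arm only. Step 5 shows that other mixes shrink, cancel or reverse it.

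It would also be tempting to conclude that the naive-only cohort must become the primary analysis. The documents do not compel that, and it would cost precision in a study already reduced from 4000 to 1600 patients. A prespecified sensitivity analysis, with prior use in the models, answers the concern.

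**What to change.** - **SAP 7.4, covariates.** Add prior oral anticoagulant use to the propensity score and to the Cox covariates, coded none / same drug / other drug. Use yes/no if the prior drug is not available or the strata are too sparse.
- **SAP 7.4, sensitivity analysis.** Prespecify a matched persistence analysis restricted to patients with no prior oral anticoagulant. It is needed alongside the covariate because the other-drug stratum would pair VKA-to-dabigatran with dabigatran-to-VKA switchers, who may not be comparable.
- **Reporting.** Give counts of pre-treated patients by arm and prior drug, so that the reader can judge the share that is only assumed above.
- **Consistency.** Reconcile SAP 6.2 with protocol 3.3.2 and 4.1.1, and list the two-month rule in SAP 4.

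The cost is SAP wording, one extra covariate and one extra matched run. The naive-only cohort will be smaller and less precise (step 6 of the working), but the main matched analysis keeps its population definition and the safety set is untouched.
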